#### **Estimation of the pooled treatment effectiveness and safety**

7. The treatment effect estimates from 3 databases will be combined using meta-analysis techniques. We will examine the heterogeneity of treatment effect using Cochrane Q statistics and I-square statistics. If there is no statistically significant evidence of treatment effect heterogeneity, we will use inverse probability fixed-effects model to pool the database-specific estimates. If there is significant treatment effect heterogeneity, we will use random-effects model.
8. Reporting of prospective monitoring results: When a statistically significant signal is detected from the pooled analysis for the primary endpoints of effectiveness or safety from pre-specified interim analysis or at the end of the data period (12/31/2020), the findings will be reported

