## **STUDY OVERVIEW AND DESIGN**

- 1. Study aims: To emulate a prospective surveillance of the effectiveness and safety of ARNI vs a comparator (ARB) in older adults with HFrEF and different frailty status.
- 2. Data source(s): Data from 2014 up to 2020 will be used.
  - a. Medicare Database
  - b. Optum Database
  - c. MarketScan Research Database
- 3. Sequential cohort monitoring design (see Figure 1): The monitoring analysis will include 1) retrospective analysis of available data (2015-2017) at the time of first analysis (January 2021) and 2) prospective analysis of new data (2018-2020) as they become available to the researchers. Within each database, we will emulate biannual updating of data by creating a propensity score (PS)-matched cohort of new users every 6-month interval, beginning on the first marketing of ARNI (July 7, 2015-December 31, 2015, and 6-month intervals afterwards). Each sequential cohort will be followed for development of the outcomes of

interest. Outcome analysis will be performed at a pre-specified 6-month interval (prospective analysis). The surveillance will be performed by frailty status (frail vs non-frail) at the time of drug initiation. The results from each database will be pooled using fixed-effects meta-analysis (assuming low heterogeneity across the databases).

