6. Adjustment for multiple testing in detecting signal: We will use the maximum sequential probability ratio testing (maxSPRT) procedure to keep the overall type-1 error rate of 0.05.  
(10)

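### Item 7 lets a heterogeneity test on three databases (2 degrees of freedom) choose the pooling model for the result item 8 relies on; one model, matched to a stated target, should be prespecified

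*Protocol*

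**What the plan says.** The Protocol's section on pooled estimation, item 7, opens: "The treatment effect estimates from 3 databases will be combined using meta-analysis techniques". It continues: "We will examine the heterogeneity of treatment effect using Cochrane Q statistics and I-square statistics". The choice of model then follows the test. On one branch, "If there is no statistically significant evidence of treatment effect heterogeneity, we will use inverse probability fixed-effects model to pool the database-specific estimates"; on the other, "If there is significant treatment effect heterogeneity, we will use random-effects model". Neither a significance level for Q, nor an I-squared cutoff, nor a random-effects estimator is given.

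Item 8 of the same section ties reporting to the pooled result: "When a statistically significant signal is detected from the pooled analysis for the primary endpoints of effectiveness or safety from pre-specified interim analysis". The final data cut is named there as a further reporting point.

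Study Overview and Design, item 3, mentions one model only: "The results from each database will be pooled using fixed-effects meta-analysis (assuming low heterogeneity across the databases").

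Error control is stated in item 6, under the within-database heading: "We will use the maximum sequential probability ratio testing (maxSPRT) procedure to keep the overall type-1 error rate of 0.05". That item does not say how the procedure applies to the pooled estimate.

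**The concern.** Fixed effects and random effects answer different questions when true effects differ between databases. The first estimates the precision-weighted average of these three databases, the second the mean effect over a population of such databases. Under item 7 the test result sets the model and so, in effect, the target.

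Three estimates carry very little information about heterogeneity. A non-significant Q will be common even when effects differ materially, so it cannot do the job of supporting fixed effects. The rule is also discontinuous: a trivial change in the database results can move Q across its cutoff and change the width of the pooled interval sharply. Analyses are repeated at 6-month intervals and by frailty status, so the model could differ between successive looks, or between frail and non-frail results that readers will compare.

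At stake are the pooled estimate and interval behind a reported finding on the primary effectiveness or safety endpoint.

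**Working it through.** **Inputs.** From the Protocol: three databases, the two-branch rule, and an overall error rate of 0.05. Assumed because the Protocol does not give them: Q tested at 0.05 (0.10 also shown), DerSimonian-Laird with a normal 95% interval for random effects, standard errors (SEs) of the log hazard ratio, and between-database SD tau. The Protocol has no pooled figure to reproduce.

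**1. Power of Q.** With three estimates and equal SEs s, Q is distributed as (1 + tau²/s²) times chi-square on 2 df, and I² = tau²/(s² + tau²). Hence P(Q > 5.991) = exp(−(5.991/2)(1 − I²)):

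- I² = 25%: exp(−2.247) = 0.106
- I² = 50%: exp(−1.498) = 0.224
- I² = 75%: exp(−0.749) = 0.473

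At level 0.10 (cutoff 4.605) the values are 0.178, 0.316 and 0.562. The largest observed I² that still selects fixed effects is 1 − 2/5.991 = 66.6% (56.6% at level 0.10).

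**2. Jump at the cutoff, equal SEs.** The DerSimonian-Laird variance is Q/2 times the fixed-effects variance, so the interval widens by √(5.991/2) = 1.73. Example with SE 0.10 in each database, chosen to sit at the cutoff:

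- Hazard ratios 0.725/0.861/1.022: Q = 5.89, p = 0.052, fixed effects, 0.861 (0.769–0.964).
- Hazard ratios 0.723/0.861/1.025: Q = 6.09, p = 0.048, random effects, 0.861 (0.707–1.049).

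**3. Unequal SEs: the estimate moves as well.** With SEs 0.05/0.12/0.15 and hazard ratios 0.85/1.08/1.16, Q = 6.48 and p = 0.039, so random effects is selected: 0.99 (0.80–1.22). Fixed effects on the same data gives 0.90 (0.83–0.98). The largest database's weight falls from 78% to 44%.

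**4. Error for the mean effect** (two-sided 0.05, single look). Fixed effects is closed form: 2[1 − Φ(1.96/√(1 + tau²·Σw²/Σw))], with w = 1/SE². At tau = 0.10:

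- SEs 0.10 each: Σw²/Σw = 100, variance ratio 2, error 0.166.
- SEs 0.05/0.10/0.15: Σw²/Σw = 315.9, variance ratio 4.159, error 0.337.

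Item 7 and random effects were simulated with 5,000,000 runs per cell.

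| Target: mean effect | tau 0 | 0.03 | 0.05 | 0.10 |
|---|---|---|---|---|
| SEs 0.10 each: item 7 | 4.8% | 5.7% | 7.3% | 13.0% |
| SEs 0.10 each: random effects always | 3.7% | 4.4% | 5.5% | 9.5% |
| SEs 0.05/0.10/0.15: item 7 | 4.8% | 7.8% | 12.7% | 23.8% |
| SEs 0.05/0.10/0.15: random effects always | 3.5% | 5.6% | 8.7% | 15.5% |

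With Q tested at 0.10, item 7 gives 11.7% and 20.9% at tau 0.10.

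**5. Error for the precision-weighted average of the three databases.** Fixed effects alone holds 5.0% at every tau. Item 7 gives 4.8% at tau 0 under both SE patterns, and 3.9% and 3.8% at tau 0.10.

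**6. Power when databases agree (tau 0).** The ratio is assumed to be 21.8%/26.5% = 0.823, borrowed for scale from the randomized trial in the Protocol's Background.

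| | Item 7 | Random always | Fixed always |
|---|---|---|---|
| SEs 0.10 each | 0.89 | 0.85 | 0.92 |
| SEs 0.05/0.10/0.15 | 0.97 | 0.93 | 0.995 |

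**The case against.** Several points on the other side stand.

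- A reader might infer that the switch is useless whichever target is meant. The figures do not support that. For the mean effect at tau 0.10, item 7 (13.0%, 23.8%) does better than fixed effects throughout (16.6%, 33.7%). When databases agree, it has about 4 points more power than random effects throughout.
- A reader might take the percentages as this surveillance's false-signal rates. They are not. Item 6 assigns signal detection to maxSPRT, and the Protocol does not equate a signal with a 95% interval that excludes 1. These are single-look rates under assumed SEs and tau.
- A reader might infer that crossing the cutoff changes only the interval. That is true of step 2 because its SEs are equal; step 3 shows otherwise. Both examples show what can happen, not how often.
- A reader might call the overview and item 7 a contradiction. The overview states its own condition of low heterogeneity and can be read as a summary of item 7's first branch. The two diverge only when Q is significant, so alignment is enough.
- A reader might infer that the switch decides whether results are published at all. Item 8 can fairly be read as reporting at the end of data in any case. The switch would then affect early reporting and the interval shown.

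The absence of the SAP does not remove the point, because the Protocol itself fixes the rule.

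**Conclusion.** The point holds as a weakness in a stated rule. A 2-df test is too weak to justify fixed effects, and it makes the model, and in effect the target, depend on the data. At an assumed tau of 0.10, one prespecified model comes closer to 5% error than the switch for either target. Random effects gives 9.5% against 13.0%, or 15.5% against 23.8%, for the mean effect. Fixed effects gives 5.0% against 3.9% or 3.8% for the average of these databases.

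The size depends wholly on the assumed SEs, tau, test level and estimator. With equal SEs and little heterogeneity the difference for the mean effect is small: item 7 has 4.8% error at tau 0 and 5.7% at tau 0.03. Confidence in the size is moderate; confidence in the description of the rule is high. The change is worth making because it costs little.

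**What to change.** - Remove the significance-test switch from item 7. State the target and prespecify one inverse-variance model for all looks and both frailty strata: fixed effects for the average of these three databases, or random effects for the mean effect across databases. The choice is the sponsor's.
- Make Study Overview and Design, item 3, agree.
- Report Q and I-squared descriptively, with the other model as a sensitivity analysis.
- If random effects is chosen, state that a normal interval with three databases still under-covers. At tau 0.10 about 56% of item 7's excess over 5% remains (4.47/7.95 points with equal SEs, 10.49/18.83 with unequal). Add an unmodified Hartung-Knapp interval as a sensitivity analysis only: its error at tau 0.10 is 5.0% and 8.0%, but its power at tau 0 is only 0.46 and 0.62.
- Replace inverse probability with inverse-variance in item 7 (terminology only).

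Cost: text edits in two sections and no new data. When the databases agree, random effects loses about 4 power points against item 7, while fixed effects gains about 3.

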## BACKGROUND

1. Angiotensin receptor blocker neprilysin inhibitor (ARNI) sacubitril/valsartan (Entresto (1))
  - a. Approved in July 7, 2015
  - b. Indication: HF with reduced ejection fraction
2. PARADIGM-HF trial; ARNI vs enalapril (2)
  - a. N=8442, follow-up 2.3 years
  - b. Composite of cardiovascular death and HF hospitalization: 21.8% vs 26.5%
  - c. Safety endpoints: hypotension (14.0% vs 9.2%), renal failure (3.3% vs 4.5%), hyperkalemia (16.1% vs 17.3%), angioedema (0.4% vs 0.2%)
3. 2017 ACC/AHA/HFSA guidelines for management of heart failure (3)
  - a. The clinical strategy of inhibition of the renin-angiotensin system with ACE inhibitors (Level of Evidence: A), OR ARBs (Level of Evidence: A), OR ARNI (Level of Evidence: B-R) in conjunction with evidence-based beta blockers, and aldosterone antagonists in selected patients, is recommended for patients with chronic HFrEF to reduce morbidity and mortality.
  - b. The use of ACE inhibitors is beneficial for patients with prior or current symptoms of chronic HFrEF to reduce morbidity and mortality (Level of Evidence: A). Although the use of an ARNI in lieu of an ACE inhibitor for HFrEF has been found to be superior, for those patients for whom ARNI is not appropriate, continued use of an ACE inhibitor for all classes of HFrEF remains strongly advised.
  - c. The use of ARBs to reduce morbidity and mortality is recommended in patients with prior or current symptoms of chronic HFrEF who are intolerant to ACE inhibitors because of cough or angioedema (Level of Evidence: A). Head-to-head comparisons of an ARB versus ARNI for HF do not exist. For those patients for whom an ACE inhibitor or ARNI is inappropriate, use of an ARB remains advised.
  - d. In patients with chronic symptomatic HFrEF NYHA class II or III who tolerate an ACE inhibitor or ARB, replacement by an ARNI is recommended to further reduce morbidity and mortality (Level of Evidence: B).

- e. ARNI should not be administered concomitantly with ACE inhibitors or within 36 hours of the last dose of an ACE inhibitor (Level of Evidence: B). Oral neprilysin inhibitors, used in combination with ACE inhibitors can lead to angioedema and concomitant use is contraindicated and should be avoided.
- f. ARNI should not be administered to patients with a history of angioedema (Level of Evidence: C).

4. 2021 ACC/AHA/HFSA focused update (4)

[figure not shown]

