## STATISTICAL ANALYSIS

### **Estimation of treatment effectiveness and safety within each database**

1. PS-matched cohorts: Within each surveillance cohort by frailty status (frail vs non-frail), we will use logistic regression that estimates the probability of receiving the drug of interest as a function of sociodemographic characteristics, diseases, prescription drugs, comorbidity index, and frailty index. Note that PS model will be fit separately by frailty status. We will perform a 1:1 ratio nearest-neighbor PS matching, with a caliper of 0.2 of the standard deviation of the logit PS (9). We will evaluate balance in covariates using standard mean difference (<0.1 is considered adequate balance) within each surveillance cohort.
2. Primary analysis for effectiveness and safety: For time-to-event analysis of the effectiveness and safety endpoints, we will use Cox proportional hazards regression to estimate the hazard ratios (HR) and 95% confidence intervals (CI) by frailty status (frail vs non-frail). The follow-up will begin on day 1 and end on the day of development of the effectiveness or safety endpoints or the earliest of the following censoring events: switching or discontinuation of the study drug, death not due to the outcome of interest, disenrollment, and end of data period (see Figure 2). Proportional hazards assumptions will be checked using Schoenfeld residuals.
3. Subgroup analyses for primary effectiveness and safety endpoints will be conducted by frailty status (frail vs non-frail):
  - a. age (65-74 years vs  $\geq 75$  years)
  - b. sex
  - c. race (black or non-black)
  - d. dual eligibility for Medicaid
  - e. major multimorbidity burden/pattern (informed by latent class analysis)
  - f. dementia (CCW definition)
  - g. HF hospitalization status ( $\geq 2$  or  $< 2$  in the past year)

4. Secondary analyses will be conducted by frailty status (frail vs non-frail):
  - a. secondary endpoints (individual components of primary effectiveness and safety composite endpoints)
5. Sensitivity analysis for primary effectiveness and safety endpoints will be conducted by frailty status (frail vs non-frail):
  - a. “intention-to-treat” analysis with a maximum follow-up time of 1 and 2 years from the index date
  - b. exposure risk window or grace period of 14 days

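### The two-stage pooling fixed in item 7 gives no weight to a database with events in one arm only, so for rare safety components, chiefly angioedema, the pooled HR can be pulled towards 1; the weighting is also misnamed

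*Protocol*

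**What the plan says.** The analysis has two stages. Within each database (Protocol, Statistical Analysis, item 2), "we will use Cox proportional hazards regression to estimate the hazard ratios (HR) and 95% confidence intervals (CI) by frailty status", after matching described as "We will perform a 1:1 ratio nearest-neighbor PS matching". Item 4.a extends the by-frailty analyses to "secondary endpoints (individual components of primary effectiveness and safety composite endpoints"; under Measurements, Outcomes, the safety components are hypotension, acute kidney injury or failure, hyperkalemia and angioedema.

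Across databases (item 7), "The treatment effect estimates from 3 databases will be combined using meta-analysis techniques". If heterogeneity is not significant, "we will use inverse probability fixed-effects model to pool the database-specific estimates". Otherwise: "If there is significant treatment effect heterogeneity, we will use random-effects model". Item 7 names no endpoints and offers no other way of pooling. Item 8 ties reporting of a signal to the primary effectiveness and safety endpoints.

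The only angioedema rates in the document are in Background, item 2.c, "angioedema (0.4% vs 0.2" per cent (ARNI versus enalapril), from the trial described in item 2.a as "N=8442, follow-up 2.3 years". The protocol states no patient numbers or expected event counts for its own cohorts.

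**The concern.** Two things are wrong with item 7 as written.

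First, the weight is misnamed. Fixed-effects meta-analysis weights each estimate by the inverse of its variance. Inverse probability weighting is a different technique, used for treatment selection or censoring.

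Second, the method suits sparse endpoints badly. If all events in a database-by-frailty stratum fall in one arm, the Cox partial likelihood has no finite maximum. The log HR runs off to infinity, its standard error with it, and the inverse-variance weight goes to zero. The random-effects option needs the same log HR and standard error, so it does not rescue the stratum.

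The loss is not neutral. If ARNI truly raises the risk, a one-sided stratum is more often ARNI-only than ARB-only, so what is lost is mainly evidence of harm. Angioedema is the rarest of the four safety components in the cited trial, and Background items 3.e and 3.f give it as a reason to restrict ARNI.

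**Working it through.** The protocol has no sample size or event count to reproduce. The check therefore uses its background rates with assumed stratum sizes and follow-up.

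**1. Mechanism.** A Cox fit to 500 versus 500 patients with 3 versus 0 events did not converge. It stopped at a log HR of about 20.6 with SE about 16,840, so the weight is 1/16,840² ≈ 3.5 × 10⁻⁹. A random-effects weight, 1/(SE² + τ²), is no larger. By contrast, a Peto calculation on the same data gives O − E = 3 − 1.5 = 1.5 and V = 3 × 0.25 = 0.75. The log HR is then 1.5/0.75 = 2.0 with SE 1/√0.75 = 1.15. The data carry information; the specified method discards it.

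**2. How often a stratum is one-sided.** Convert the rates to constant hazards: −ln(1 − 0.004)/2.3 = 0.00174 per year for ARNI, and −ln(1 − 0.002)/2.3 = 0.00087 per year for the comparator. With n pairs followed for t years, the expected events are close to a = 0.00174·n·t and b = 0.00087·n·t. Then

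P(events in one arm only) ≈ e^(−a)(1 − e^(−b)) + e^(−b)(1 − e^(−a)).

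For n = 500 and t = 0.5, a = 0.435 and b = 0.218, so P = 0.647 × 0.196 + 0.804 × 0.353 = 0.41.

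| Pairs per stratum | Expected events at 0.5 year | One arm only, 0.5 year | Both arms empty, 0.5 year | One arm only, 1 year |
|---|---|---|---|---|
| 500 | 0.44 vs 0.22 | 41% | 52% | 52% |
| 1,000 | 0.87 vs 0.44 | 52% | 27% | 45% |
| 2,000 | 1.74 vs 0.87 | 45% | 7% | 20% |
| 5,000 | 4.36 vs 2.18 | 12% | 0.1% | 1% |
| 10,000 | 8.71 vs 4.35 | 1% | 0% | 0% |

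**3. Effect on the pooled estimate.** Poisson counts were simulated for three databases with equal person-time in the two arms and a true ratio of 2 (200,000 runs per setting). Log rate ratios stood in for Cox log HRs. Inverse-variance pooling without the one-sided databases was compared with the ratio of events summed over databases. With equal person-time that ratio is the Mantel-Haenszel rate ratio.

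| Expected comparator events in the three databases | Runs with a one-sided database | Events discarded | Median, inverse variance | Median, count analysis |
|---|---|---|---|---|
| 1, 0.5, 0.5 | 87% | 41% | 1.25 | 2.0 |
| 2, 1, 1 | 70% | 19% | 1.60 | 2.0 |
| 4, 1, 1 | 65% | 10.5% | 1.81 | 2.0 |
| 10, 3, 3 | 10% | 1.3% | 1.92 | 2.0 |
| 20, 8, 8 | 0.1% | under 0.1% | 1.97 | 2.0 |

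Medians are over runs that yield an estimate. In the first row, inverse-variance pooling yields none in 26% of runs. The count analysis yields no finite ratio in 1 − (1 − e^(−2))(1 − e^(−4)) = 15%. In that row 36% of databases were ARNI-only and 12.5% ARB-only, which explains the direction.

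In the last two rows almost nothing is discarded, so the remaining shift comes from the inverse-variance weights themselves: with few events, the larger ratios get the larger variances. The count analysis removes that shift as well.

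**The case against.** **Handling of empty arms belongs in an SAP, which is not shown.** This stands against any complaint that a zero-event rule is missing. It does not answer the point here: item 7 fixes a method, and a workable rule for one-sided strata would have to depart from it.

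**Item 7 does not name the components.** True. Item 4.a sits under the within-database heading, so applying item 7 to angioedema is a reading of an unqualified sentence. It is the natural reading, since no other pooling method is given.

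**The damage is small beside the imprecision.** Largely right at moderate counts. With 3.8 expected ARB and 7.6 ARNI events, the SE of the log ratio is √(1/3.8 + 1/7.6) = 0.63, and an approximate 95% interval around 2 is 0.58 to 6.9. A shift from 2.0 to 1.9 hardly matters against that. With total expected comparator events of two, no estimator is informative. Still, the shift is systematic, points towards no difference, and costs little to avoid.

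**Stronger readings that the document does not support.** A reader might infer that databases will be dropped; without patient counts one can say only that they can be. A reader might also quote the chance that at least one arm is empty, 93%, 80% and 52% at 500, 1,000 and 2,000 pairs over 0.5 year. Those figures include strata with both arms empty, which carry no information on the ratio under any method.

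Nor does the problem extend to early results in general. At the background rates for cardiovascular death or HF hospitalization over 0.25 year, the one-sided chance is 10% at 100 patients per arm and 0.15% at 250, and the first actual analysis already holds 2015-2017 data.

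**Conclusion.** The point holds in a limited form. The weight in item 7 is misnamed, and the pooling method is poorly suited to the rarest safety component. For angioedema, one-sided strata are likely at about 500 to 2,000 pairs with 0.5 to 1 year of follow-up (20% to 52%). They are rare from about 5,000 pairs at 1 year. With a true HR of 2 the median pooled HR is about 1.25 in the sparsest setting shown and about 1.9 at moderate counts.

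The consequence is confined to secondary component estimates. Angioedema alone cannot trigger a report under item 8, and its events still count in the primary safety composite.

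These sizes rest on assumed pair numbers and follow-up, and on rates from a trial with an enalapril comparator standing in for ARB users. The requirement for a primary-position hospital or ED code and the exclusion of earlier angioedema would lower the counts; an older or frailer population could raise them.

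**What to change.** In item 7, replace inverse probability with inverse variance. Add one sentence: for angioedema, at every look, results are pooled across databases by a Mantel-Haenszel person-time rate ratio, or by exact conditional Poisson regression, stratified by database and reported separately for frail and non-frail patients.

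Name the endpoint in advance rather than switching on an observed event count, so that the effect measure does not change from look to look. Do not pool across frailty, because the aim and all analyses are by frailty status. If other components are expected to be as sparse, name them in the same sentence.

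The cost is that sentence and a standard routine that needs only events and person-time per arm from each database, so no patient-level data have to be shared. The downside is a rate ratio rather than a Cox HR for that component.

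### Results may be reported at an interim signal, but the only estimate defined is the ordinary pooled Cox hazard ratio with a 95% interval; only the test is adjusted for repeated looks

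*Protocol*

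**What the plan says.** Four items of the protocol's Statistical Analysis bear on this.

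- Item 2 defines the estimator and its interval: "we will use Cox proportional hazards regression to estimate the hazard ratios (HR) and 95% confidence intervals (CI) by frailty status".
- Item 6 brings in maxSPRT under the label "Adjustment for multiple testing in detecting signal", as a "procedure to keep the overall type-1 error rate of 0.05". It concerns the test; it does not mention the estimate or the interval.
- Item 7 combines the databases: "we will use inverse probability fixed-effects model to pool the database-specific estimates", or a random-effects model if heterogeneity is significant. Again there is no adjustment for repeated looks.
- Item 8 names two reporting occasions. The first is "When a statistically significant signal is detected from the pooled analysis for the primary endpoints of effectiveness or safety from pre-specified interim analysis". The second is the end of data, since the sentence runs on: "from pre-specified interim analysis or at the end of the data period (12/31/2020), the findings will be reported".

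On timing, Study Overview and Design says "Outcome analysis will be performed at a pre-specified 6-month interval (prospective analysis"), with cohorts formed "beginning on the first marketing of ARNI (July 7, 2015-December 31, 2015, and 6-month intervals afterwards"). The same paragraph describes 2015-2017 as a retrospective analysis of data already in hand and 2018-2020 as prospective. The documents therefore allow 11 looks (one per half-year) or 7 (2015-2017 as one look, then six half-years).

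**The concern.** A sequential boundary that holds the error rate of the test does nothing for the estimate taken when the boundary is crossed. That estimate was selected for being extreme, so on average it lies further from 1 than the truth, most of all at looks with few events. A fixed-sample 95% interval around it has no guarantee of 95% coverage.

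This is more than a detail left open for a statistical analysis plan. The protocol itself fixes the estimator, the interval and a data-dependent reporting trigger, and followed as written these produce the effect. Item 8 joins its two occasions with *or*, so after an interim signal it does not commit to a full-data estimate or say which estimate is primary. The aim is to describe benefit and harm in frail and non-frail patients, so the size of the effect matters as much as the signal.

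**Working it through.** **The plan's own figure.** The only design figure is the overall type-1 error of 0.05. It cannot be reproduced, because no critical value, sidedness or number of looks is given. The check instead calibrates a boundary to 0.05.

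**Inputs from the protocol.** Overall error 0.05; 1:1 matching; 6-monthly looks from the second half of 2015 to 12/31/2020; ordinary hazard ratio and 95% interval.

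**Assumptions, not in the protocol.** Two-sided test; boundary flat in z (the normal approximation to maxSPRT, where the log-likelihood ratio is z²/2); events accruing evenly; total events D per frailty stratum of 500, 1,000 or 2,000; true hazard ratio mainly 0.90; report at the first crossing, otherwise at the end.

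**Formulas.** With a fraction t of the events observed, the standard error of log HR is 2/√(D·t). A signal of benefit needs HR ≤ exp(−c·2/√(D·t)). Calibrating to 0.05 gives c ≈ 2.57 for 11 equal looks and c ≈ 2.36 for 7 looks with the first at t = 5/11.

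**Direct calculation, D = 1,000.**
- 11 looks, third look: 1,000 × 3/11 = 273 events; exp(−2.57 × 2/√273) = exp(−0.311) = 0.73.
- 7 looks, first look: 1,000 × 5/11 = 455 events; exp(−2.36 × 2/√455) = exp(−0.221) = 0.80.

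Any benefit signal at those looks must show 0.73 or less, or 0.80 or less, even if the truth is 0.90.

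**Simulation, 400,000 paths, true HR 0.90.** Means are geometric; an early signal is one before the last look.

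| Looks | Events | Early signal | Mean HR at early signal | Coverage in those reports | Mean HR, all reports | Coverage, all reports |
|---|---|---|---|---|---|---|
| 11 | 500 | 14% | 0.67 | 48% | 0.88 | 90% |
| 11 | 1,000 | 25% | 0.75 | 75% | 0.88 | 91% |
| 11 | 2,000 | 47% | 0.82 | 89% | 0.87 | 92% |
| 7 | 500 | 17% | 0.74 | 81% | 0.89 | 94% |
| 7 | 1,000 | 30% | 0.80 | 91% | 0.89 | 95% |
| 7 | 2,000 | 54% | 0.85 | 95% | 0.89 | 95% |

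The 0.67 in the first row becomes 0.68 if signals at the last look are counted too.

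**Clear effect, many events (true HR 0.80, D = 2,000).** Mean HR at an early signal is 0.76 (11 looks) or 0.80 (7 looks); coverage over all reports is about 96% in both.

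**No effect (true HR 1.0).** Coverage over all reports is 92% (11 looks) or 93% (7 looks).

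**Remedies.** The full-data estimate, taken whatever happened at the interims, averages 0.90 when the truth is 0.90 and covers at 95%. A repeated interval replaces 1.96 by c: 2.57/1.96 = 1.31 and 2.36/1.96 ≈ 1.2, so it is about 31% or 21% wider on the log scale.

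**The case against.** - **Adjusted estimation belongs in a statistical analysis plan, which is not shown.** A bare omission would be no finding. This one stands because the protocol states the estimator, the interval and the trigger. It remains true that a separate plan could already deal with it, so exaggeration in print is a risk and not an established fact.
- **Item 8 also reports at the end of data.** Correct. A reader might infer that surveillance stops at the first signal, or that the full-data estimate is then withheld. No passage says either, and the design section plans analysis of 2018-2020 data without such a condition. What stands is only that the full-data report is not promised after a signal.
- **Eleven looks is the worse case.** Also correct. Under the 7-look reading the earliest looks do not exist, and for a true HR of 0.90 coverage over all reports is 94-95%.
- **Selecting on significance inflates any study.** A single fixed analysis with 1,000 events and true HR 0.90 averages 0.845 among its significant results. The like-for-like means, given any signal, are 0.76 (11 looks) and 0.81 (7 looks), so only the difference belongs to the sequential rule.
- **Comparison across frailty strata.** A reader might infer that one stratum will be read at its signal beside the other at a later look. The protocol runs surveillance by frailty status at each interval and nowhere says this, so distortion of the comparison is not shown.

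**Conclusion.** The point holds as a gap in item 8 that should be closed. As written, a hazard ratio reported at an interim signal is exaggerated on average. For an assumed true HR of 0.90 the mean at an early signal is about 0.67 to 0.82 with 11 looks, or 0.74 to 0.85 with 7, as events run from 500 to 2,000. Averaged over all reports the shift is slight (0.87 to 0.89), with coverage of 90-92% or 94-95%.

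The flat statement that the interval does not cover at 95% goes too far. Under-coverage is marked for few events, weak effects or early looks, and disappears with many events and a clear effect, where coverage can slightly exceed 95%. All sizes depend on the assumed events, effect, sidedness and boundary shape, and on which look schedule the design section means.

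**What to change.** Amend item 8 to say that:

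(a) analysis of every primary endpoint in both frailty strata continues to 12/31/2020 whatever the interim signals, and the full-data pooled hazard ratio at that common cut-off is reported as the primary effect estimate;

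(b) any signal report before then gives the test result with a repeated confidence interval matched to the boundary, and labels the hazard ratio as an interim estimate.

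Part (b) repairs the interval's overall coverage but does not remove the bias in the point estimate; part (a) supplies an estimate free of that selection. A median-unbiased estimate in the signal report is optional.

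The cost is a few sentences and no new data, since data through 2020 are already planned. The interval in an early report becomes about 21-31% wider on the log hazard ratio scale.
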